APPENDIX A: DBS CMV PCR ASSAY COMPARISON

Description	Procedure in Publication	Current Procedure
Filter paper used	Whatman FTA Elute cards	Whatman 903 Protein Saver cards
Size of each punch	3 mm in diameter	6 mm in diameter
Number of punchs used for DNA extraction	4	2
PCR master mix	QuantiTect Muliplex PCR mix with ROX	QuantiTect Muliplex PCR NoROX mix
PCR Machine	7900HT sequence detection system	QuantStudio 7 flex real-time PCR system
IU conversion	1 IU= 4 copies (AcroMetrix)*	1 IU=1.4 copies (WHO)
Internal control template	Spiked into PCR master mix	Spike into extraction lysis buffer
Internal control primers and probe	EXO	EXO BS
DNA Elution volume	100 ul	100 ul
Amount of DNA used for each PCR	20 ul	20 ul
CMV primers and probe	gB and IE-EX4	gB and IE-EX4
CMV PCR standard	1e1 to 1e5	1e1 to 1e5

DMID Protocol Number 16-0098
CMV DBS Testing in HCT Recipients

APPENDIX B: DEFINITION OF END-ORGAN CMV DISEASE

CMV Disease	Clinical Signs and Symptoms	Proven	Probable	Note
Pneumonia	Pneumonia (e.g. new infiltrates on imaging, hypoxia, tachypnea and/or dyspnea)	Clinical signs and symptoms with CMV in lung tissue by virus isolation, rapid culture, histopathology, IHC, or DNA hybridization	Clinical signs and symptoms with detection of CMV by viral isolation, rapid culture of BALF, quantitation of CMV DNA in bronchoalveolar lavage fluid (BALF)	Quantitative PCR on lung tissue could be defined as "possible"
Gastrointestinal (GI) disease	Upper and/or lower GI symptoms	Clinical signs and symptoms with macroscopic mucosal lesions plus CMV documented in tissue by virus isolation, rapid culture, histopathology, IHC, or DNA hybridization	Clinical signs and symptoms with CMV documented in tissue but without the requirement for macroscopic mucosal lesions	CMV documented in blood by NAT (PCR) or Ag or PCR from tissue is not sufficient for CMV GI disease diagnosis. These could be defined as "possible".
Retinitis	Retinitis	Judged by an ophthalmologist	Not used	Diagnosis could be supported by vitreous fluid by NAT (PCR)
Encephalitis/ Ventriculitis	Central nervous system (CNS) symptoms	Clinical signs and symptoms with CMV documented in tissue by virus isolation, rapid culture, histopathology, IHC, or DNA hybridization	Clinical signs and symptoms with CMV documented in in CSF without visible contamination plus abnormal imaging or EEG	Not used
Other Organs ³⁵	Most organs	Clinical signs and symptoms with CMV documented in tissue by virus isolation, rapid culture, histopathology, IHC, or DNA hybridization	Not used	Not used

APPENDIX C: SCHEDULE OF EVENTS

			In	itial St	tudy Vi	sit ³						
Visit/Contact	Screening ¹	Enrollment ²	Training 1 ⁵	Training 2 ⁶	Training 3 ⁷	Discharge	DBS self- collection	Plasma Collection ⁴	Quarterly Contact 1	Quarterly Contact 2	Quarterly Contact 3	Final Study Visit
Days after HCT	60-180						60-365	60-365	90	180	270	365
Window (days)		N/2	4						±14	±14	±14	(+120)
Confirm informed consent		Х										
Eligibility assessment	X, Z											
Randomization		Х										
Review of medical history		X, Z										
Review of concomitant medication		X, Z				Х			Х	Х	Х	X, Z
Confirm CMV monitoring interval						Χ, Ζ			Х	Х	Х	
Adherence counseling ⁸			Х									
DBS collection and website training ⁹			Y	Y	Y		Y ¹⁰					
Provision of initial study kits						Y						

¹ It is recommended to have screening done approximately one month prior to planned discharge from the primary transplant clinic

² Screening, enrollment, and initial study visit (trainings for DBS arm) may occur on the same day as long as all trainings are completed by subjects with proficiency and confirmed by study personnel prior to discharge from primary transplant clinic.

³ Trainings 1-3 must be completed prior to planned discharge from the subject's primary transplant clinic.

⁴ Confirmatory plasma sample will be collected from DBS arm subjects if they had a CMV positive DBS.

⁵ Training with study staff supervision.

⁶ Training with study staff supervision.

⁷ Training without study staff supervision.

⁸ Adherence counseling should be done on all randomized subjects after enrollment but prior to discharge from primary transplant clinic.

⁹ DBS collection is required at each DBS training visit. Website and mobile technology training may be optional for training 2 and 3 as necessary.

¹⁰ DBS collection starts the week after discharge and ends approximately one-year post-HSCT

DMID Protocol Number 16-0098 CMV DBS Testing in HCT Recipients

Version 5.0 30 June 2022

			In	itial St	tudy Vi	isit ³						
Visit/Contact	Screening ¹	Enrollment ²	Training 1 ⁵	Training 2 ⁶	Training 3 ⁷	Discharge	DBS self- collection	Plasma Collection ⁴	Quarterly Contact 1	Quarterly Contact 2	Quarterly Contact 3	Final Study Visit
Days after HCT		60-180						60-365	90	180	270	365
Window (days)		N/A							±14	±14	±14	(+120)
Kit integrity monitoring ¹¹						Y	Y					
Subject questionnaire ¹²						Y	Y					Y
Provider questionnaire ¹³												Y
Safety monitoring									Х	Х	Х	Х
Obtain interim medical records ¹⁴									Х	Х	Х	X, Z

X = performed for all randomized subjects

Y = performed for DBS arm subjects only

Z = performed for observational cohort only

GRAY columns may not be required. Depending on when a subject enrolls in the study, the duration of participation will be between 26 and 44 weeks. Columns marked in GRAY apply to those subjects whose participation includes these time points. If the scheduled quarterly visit is within 10 days of subject randomization, the corresponding quarterly visit will be waived.

¹¹ Subjects are instructed to report of any failures in DBS kits during the duration of study participation. At each time of subject reporting, study staff is responsible for uploading the reported information to Advantage eClinical eCRF. If reported problem meets adverse (AE) criteria, a separate AE form must be submitted.

[figure not shown]
¹² Patient questionnaire will be given after 3rd training session, 1 month after discharge, and at the end of study.

¹³ Primary care providers will be given a questionnaire at the time of last quarterly contact for medical records review.

¹⁴ Obtain CMV testing frequency and results, presence of CMV disease, use of antivirals of CMV treatment, and use of steroids for GVHD

[figure not shown]
APPENDIX D: SAFETY REPORTING

1. Adverse Event

Is the event considered Unexpected?

DMID/NIAID/NIH CONFIDENTIAL

The Statistical Analysis Plan (SAP) for "A Multi-Site, Randomized Trial of Subject-Collected Dried Blood Spot CMV Testing with Mobile Technology Support to Optimize Preemptive Therapy Later After Allogeneic HCT" (DMID protocol 16-0098) describes and expands upon the statistical information presented in the protocol. This document describes all planned analyses and provides reasons and justifications for these analyses. It also includes sample tables, listings, and figures planned for the final analyses. Regarding the final analyses and Clinical Study Report (CSR), this SAP follows the International Conference on Harmonisation of Technical Requirements for Registration of Pharmaceuticals for Human Use (ICH) Guidelines, as indicated in Topic E3 (Structure and Content of Clinical Study Reports), and more generally is consistent with Topic E8 (General Considerations for Clinical Trials) and Topic E9 (Statistical Principles for Clinical Trials). The structure and content of the SAP provides sufficient detail to meet the requirements identified by the FDA and ICH, while all work planned and reported for this SAP will follow internationally accepted guidelines published by the American Statistical Association and the Royal Statistical Society for statistical practice.

This document contains four sections: (1) a review of the study design, (2) general statistical considerations, (3) comprehensive statistical analysis methods for efficacy and safety outcomes, and (4) a list of proposed tables and figures. Within the table and figure mock-ups (Appendices 1 and 2), references to CSR sections are included. Changes to the planned analyses described in this SAP would be included in amendment(s) to the SAP or described and justified in the CSR, as appropriate. The reader of this SAP is encouraged to also review the study protocol for details on conduct of the study and the operational aspects of clinical assessments.

2. INTRODUCTION

Despite strong evidence that preemptive therapy is highly effective in preventing cytomegalovirus (CMV) end organ disease after hematopoietic cell transplant (HCT), CMV monitoring adherence decreases significantly after day 100, when patients typically leave the care of the transplant team. Outside of the clinical trial setting, the requirement for weekly blood draws is burdensome for patients late after HCT. Finger-stick collected DBS CMV testing would allow participants to collect their samples at home and mail the cards directly to the laboratory. In addition, mobile technology can be used to automate simple reminder and notification systems and to facilitate ongoing communication among the patient, their primary oncologist, and the transplant center.

This study is a multi-site randomized trial where participants are randomized to either participant-collected DBS CMV testing with mobile technology support or standard of care to optimize preemptive therapy late after allogeneic HCT. 150 allogeneic HCT recipients \geq 15 years of age, who are considered by their transplant team to be at risk for late CMV disease and are recommended to continue CMV monitoring after day 100 post-transplant will be randomized and will be followed from discharge to 365 days post-transplant. The primary aim of the study is to evaluate adherence to recommended CMV monitoring during the first year after transplant upon enrollment.

2.1. Purpose of the Analyses

This Statistical Analysis Plan describes the data and analyses that will be included in the final clinical study report. Analyses planned for presentation to the Data and Safety Monitoring Board (DSMB) meetings are described in a separate DSMB report shell document.

3. STUDY OBJECTIVES AND ENDPOINTS

3.1. Study Objectives

3.1.1. Primary Objective

To evaluate adherence to recommended CMV monitoring duration and interval during the first year after HCT upon enrollment using participant collected dried blood spot testing.

3.1.2. Secondary Objectives

- 1. Evaluate the mean difference between the recommended monitoring that each participant completes between the DBS and the control arm
- 2. Compare the incidence of CMV disease between the DBS monitoring and standard of care arms
- 3. Evaluate the safety of DBS monitoring

3.1.3. Exploratory Objectives

- 1. Evaluate the transit time from self-collection to arrival in the laboratory
- 2. Assess the mechanism for non-compliance as defined by a missing DBS sample PCR result (e.g. mobile technology failure, sample collection failure, sample delivery failure, sample viability failure)
- 3. Compare the performance characteristics of concurrently drawn DBS with plasma CMV PCR (e.g., sensitivity and specificity concordance)
- 4. Determine if the randomized study population is representative of the population as a whole
- 5. Obtain a population-based estimate of late CMV disease in observational and randomized cohorts
- 6. Describe local provider CMV treatment algorithms
- 7. Assess participant and provider satisfaction of DBS testing

3.2. Outcome Measures

3.2.1. Primary Outcome Measures

The number of participants who have completed >90% of their recommended CMV monitoring tests at one year after HCT in the DBS and control arms

3.2.2. Secondary Outcome Measures

- 1. The total number of recommended CMV monitoring tests that were completed per participant by 1 year after HCT
- 2. Number of participants in DBS and standard of care arms with end-organ CMV disease, possible and proven/probable by 1 year after HCT; CMV syndrome will not be used to define CMV disease
- 3. Number of participants with finger-stick procedure-related Grade 3 AEs at 1 year after HCT

3.2.3. Exploratory Outcome Measures

- 1. Mean time from scheduled pick-up at participant residence (DBS tests) or blood draw facility (plasma sample) to arrival at the laboratory (hours) at all applicable test points throughout the study period
- 2. Number of mobile technology failures, sample collection failures, sample delivery failures, and sample viability failures.
- 3. Sensitivity, specificity and predictive values of CMV detection in DBS versus plasma testing
- 4. Number and type of key transplant characteristics in randomized participants and observational participants
- 5. Describe the baseline participant demographics of randomized cohort and observational cohort.
- 6. Number of participants with end-organ CMV disease (possible and proven/possible) at 1 year after HCT in randomized participants and observational participants
- 7. Describe local provider CMV treatment viral load treatment thresholds
- 8. Describe local provider CMV monitoring interval recommendations
- 9. Report composite scores of different variables of participant and provider satisfactions according to the 5-point Likert scale questionnaires.

3.3. Study Definitions and Derived Variables

3.3.1. End of Follow-up

End of follow-up is defined as the day of protocol completion for those who completed the protocol or the day of early termination for those who have withdrawn from the study. If participants withdrew from DBS collection but agreed to have their medical charts reviewed, end of follow-up will still be considered as the date of withdrawal for adherence and DBS collection compliance analyses because they didn't receive intended intervention after withdrawal. The end of follow-up for these participants for safety analyses will be the date of last medical chart review.

3.3.2. Study Period

The study period for all safety analyses is defined as the time from enrollment to End of Follow-up.

The study period for all adherence analyses and DBS collection compliance analyses is the time from discharge to End of Follow-up. For participants in the DBS arm who were hospitalized during the follow-up, the duration of hospitalization will be subtracted from the study period for assessment of compliance with DBS collection.

3.3.3. Maximal Possible Study Period

The maximal possible study period is defined as the time from enrollment to end of maximal possible followup time, which is 1 year after HCT, or the date of death if a participant died during the follow-up. If a participant completed the study, the maximal possible study period will be the same as the study period defined in Section 3.3.2.

Sensitivity analyses for the primary outcomes will be conducted with ITT and mITT populations in the follow-up time between discharge and the end of the maximal possible study period.

If a participants withdrew from the DBS collection but agreed to have their medical chart reviewed, the clinician recommended monitoring interval after withdrawal will be used to calculate the number of recommended monitoring tests, until the end of maximal possible study period.

If a participant withdrew from the study and didn't agree to have their medical chart reviewed, the lastobserved clinician-recommended interval prior to withdrawal of consent will be carried over to the remainder of the maximal possible study period and number of clinician-recommended monitoring test will be calculated with the method described in Section 3.3.4 and Appendix 4.

3.3.4. Number of Clinician-Recommended CMV Monitoring Tests Expected

At discharge, the clinician-recommended CMV monitoring schedule is anticipated to be weekly, however during the course of the study the participant's clinical team may recommend that monitoring become less frequent, for example at bi-weekly, monthly, quarterly or other schedules. The recommended monitoring schedules and the dates on which they come into effect are entered into the data system on the Visit Documentation electronic Case Report Form (eCRF) at discharge, each quarterly contact, or as needed between quarterly contacts, during medical chart abstraction. Letting *d* represent the number of days between clinician recommended CMV monitoring tests in the new schedule, the number of expected tests will be calculated using the following assumptions:

- 1. The first expected test occurs d days after discharge.
- 2. If the monitoring frequency is reduced, then the first test for the next schedule is expected d days after the last expected test in the previous interval.
- 3. If the monitoring frequency is increased, then the first test for the new schedule is expected d days after the date that the recommended interval was changed.

The number of expected tests during the study period for a given participant is the sum of the number of expected tests during each monitoring schedule over the course of the study period (defined in Section 3.3.2). Detailed information for the calculations of the number of expected tests can be found in Appendix 4.

At the University of Minnesota, the clinician recommended CMV monitoring schedule was not recorded, so this site entered the actual number of monitoring tests instead. These data will be used for the primary adherence analysis in the ITT population. A sensitivity analysis will be conducted to exclude all participants from the University of Minnesota for the primary and secondary adherence measures along with the local provider CMV monitoring interval recommendations summary (See Section 6.4, Section 8, and Section 14 for further details).

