3 OBJECTIVES

3.1 Study Objectives

3.1.1 Primary Hypothesis

Home-based, mobile technology supported virologic monitoring will result in adherence rates associated with effective preemptive strategies against late CMV end organ disease

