3.3.5. Number of Clinician-Recommended CMV Monitoring Tests Completed

The clinician-recommended CMV monitoring tests actually completed are entered into the data system on the CMV Test Results (CTR) – Chart Review eCRF. The number of tests completed will be the number of records entered on this eCRF that were collected on or prior to the end of follow up date or, as a sensitivity analysis, the maximal possible study period end date.

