5. SAMPLE SIZE CONSIDERATIONS

Power calculations used a binomial distribution to ascertain the number of participants needed to detect a clinically meaningful difference in proportions of participants meeting the primary endpoint [10]. Based on preliminary data, the assumed proportion of individuals completing >90% of their recommended surveillance tests in the standard office-based testing arm would be in the range of 50-55%. In a previously reported clinical trial, high proportions of CMV monitoring completion resulted in the clinically relevant outcome of a low incidence of late CMV disease [1]. To be successful, this proof-of-concept trial needs to demonstrate that similarly high proportions of monitoring can be achieved with participant collected DBS monitoring. With 150 participants, randomized 2:1, there will be 90-96% power to detect an absolute difference in testing proportions of 25-30% between participants in the intervention (80% with >90% adherence rate) and control arms (50% with >90% adherence rate) (Table 2. Although the 2:1 randomization does not result in increased statistical power, randomizations that favor the experimental arm (2:1 or 3:1) appear to increase the appeal to the potential study participant and have been used successfully in several recent multicenter CMV randomized trials [4, 2, 12].

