6.4. Covariates and Subgroups

As randomization was stratified by transplant site and participant's perceived ease of access to blood draw facility, transplant site and participant's perceived ease of access to blood draw facility are included as covariates in the logistic regression used to conduct the primary analysis.

The protocol does not define any formal subgroup analyses and the study is not adequately powered to perform subgroup analyses. However, a sensitivity analysis will be conducted for the adherence outcome measures to exclude all participants from the University of Minnesota, as this site entered actual number of monitoring tests into the recommended monitoring schedule.

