8.1. Primary Adherence Analysis

A traditional logistic regression model will be fit to the ITT population where the outcome is whether or not the participants completed > 90% of their clinician-recommended CMV monitoring tests in the study period by 1-year after HCT. A two-sided Wald-test for evidence of a non-zero coefficient for intervention group in the regression will be conducted at the 5% significance level. This analysis will be repeated in the mITT population and the Completer population. The summary of the primary adherence analysis results will be presented in Table 14.

A sensitivity analysis, logistic regression will be fit in the ITT and mITT populations with the maximal possible study period, where the outcome is whether or not the participant completed > 90% of their recommended monitoring tests by the end of maximal possible study period. These results will be presented in Table 15.

In addition, as a sensitivity analysis, logistic regression will be fit in the ITT and mITT populations excluding all participants from the University of Minnesota (See Section 6.4), where the outcome is whether or not the participant completed > 90% of their recommended monitoring tests by 1-year after HCT. These results will be presented in Table 16. Example SAS code for this analysis is included below and specifies the INFLUENCE option to display regression diagnostics and the PARAM=REF option to obtain parameter estimates appropriate to the reference coding where the regression coefficient and odds ratio are estimated for the effect of the intervention compared to the standard of care.

ODS GRAPHICS ON;

PROC LOGISTIC DATA=DSN;

CLASS TRT SITE EASE / PARAM=REF;

MODEL SUCCESS = TRT SITE EASE /INFLUENCE IPLOTS;

RUN;

ODS GRAPHICS OFF;

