All Randomized (N = X)	No Further Monitoring Required	XXX	XX.X	xxx	xx.x	xxx	xx.x	xxx	xx.x	xxx	xx.x	xxx	xx.x	xxx	xx.x
	Weekly	XXX	XX.X	xxx	XX.X	xxx	xx.x	xxx	XX.X	xxx	XX.X	xxx	XX.X	xxx	XX.X

	Least-Frequent Clinician- Recommended Monitoring Interval	Transplant Site										se of Access ing Univers			ity
Treatment Arm		Clinician- Recommended Cancer Research Center							MD Anderson Cancer Center		isy	Difficult		Ove	erall
		n	%	n	%	n	%	n	%	n	%	n	%	n	%
	Bi-Weekly	xxx	xx.x	xxx	xx.x	xxx	xx.x	XXX	xx.x	XXX	xx.x	xxx	xx.x	xxx	xx.x
	Monthly	xxx	xx.x	xxx	xx.x	xxx	xx.x	XXX	xx.x	XXX	xx.x	xxx	xx.x	xxx	xx.x
	Quarterly	xxx	XX.X	xxx	XX.X	XXX	XX.X	XXX	XX.X	XXX	XX.X	XXX	xx.x	xxx	XX.X

N=Number of participants in the ITT Population with recommended in-office CMV monitoring intervals recorded.

n = Number of participants with results reported for the clinician-recommended CMV monitoring intervals, excluding monitoring intervals of "Other".

^aThe University of Minnesota entered the actual number of clinician-recommended CMV monitoring tests instead of the expected number of clinician-recommended CMV monitoring tests.

Tables with similar format:

[figure not shown]
- Table 43:Least Frequent Clinician-Recommended Interval Categories by 180 Days Post-HCT, by Intervention Group and Stratification
Variables
- Table 44:Least Frequent Clinician-Recommended Interval Categories by 270 Days Post HCT, by Intervention Group and Stratification
Variables
- Table 45:Least Frequent Clinician-Recommended Interval Categories by 365 Days Post-HCT, by Intervention Group and Stratification
Variables

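### One of the four sites recorded tests done in place of the recommended schedule, yet it stays in the primary ITT analysis, so >90% adherence is not validly measured there

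*SAP*

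**What the plan says.** SAP 4.5.1 defines success as completing more than 90% of the clinician-recommended tests, that is, tests completed divided by tests recommended. For the numerator, SAP 3.3.5 counts chart-review entries: "The number of tests completed will be the number of records entered on this eCRF". The denominator comes from the recommended intervals and the dates on which they changed (SAP 3.3.4, Appendix 4).

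At the University of Minnesota the recommended schedule was not recorded. SAP 6.4 says that "this site entered actual number of monitoring tests into the recommended monitoring schedule", and the Table 42 footnote says that the "University of Minnesota entered the actual number of clinician-recommended CMV monitoring tests instead of the expected number of clinician-recommended CMV monitoring tests". SAP 14 adds that the number entered was of tests completed. SAP 3.3.4 nevertheless says of these entries: "These data will be used for the primary adherence analysis in the ITT population".

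The site is removed only in a secondary role. SAP 8.1 says that "as a sensitivity analysis, logistic regression will be fit in the ITT and mITT populations excluding all participants from the University of Minnesota", with results in Table 16; Table 19 does the same for the secondary adherence outcome.

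**The concern.** The trial exists to detect missed recommended tests. If tests done stand in both the numerator and the denominator, a missed test cannot be seen. The site then contributes outcomes to the primary result that do not measure adherence.

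The level of adherence matters as well as the difference between arms. The protocol's primary hypothesis is that home-based monitoring "will result in adherence rates associated with effective preemptive strategies against late CMV end organ disease", and the SAP's sample size section says that the trial "needs to demonstrate that similarly high proportions of monitoring can be achieved with participant collected DBS monitoring". Table 14 is where that level will be read. Its shell carries no footnote on the site, and nothing says which result governs if Tables 14 and 16 disagree. Power is also at stake, since all 150 participants are counted as informative.

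**Working it through.** **Inputs from the documents.** 100 DBS and 50 standard-of-care participants (SAP 4.4.3); 80% v 50% or 55% reaching >90% adherence (SAP 5, Table 2); two-sided 5% Wald test from a logistic model with site and ease of access (SAP 8.1); four sites (Protocol 11.3).

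**Assumptions, not in the documents.** The site's share of randomised participants, *s*, is 25% (range 10% to 40%). Its denominator is the entered count, and that count agrees with the chart records.

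**1. The stated power.** The SAP says that "there will be 90-96% power to detect an absolute difference in testing proportions of 25-30" percentage points. With pooled variance and no continuity correction, power = Φ[(p₁ − p₀ − 1.96·SE₀)/SE₁], where SE₀ = √[p̄(1−p̄)(1/n₁+1/n₀)] and SE₁ = √[p₁(1−p₁)/n₁ + p₀(1−p₀)/n₀].
- 80% v 50%: p̄ = 105/150 = 0.70; SE₀ = √(0.21 × 0.03) = 0.0794; SE₁ = √(0.0016 + 0.0050) = 0.0812; (0.30 − 0.1556)/0.0812 = 1.78; power 96.2%.
- 80% v 55%: 88.5%. 80% v 58%: 80.3%.

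The stated 96%, 89% and 80% are reproduced.

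**2. The endpoint at this site.** Protocol 11.1.1 gives an example with 38 weekly tests expected. Someone who does 19 of them has 19/38 = 50% and fails. If 19 is entered as the expected number, the ratio is 19/19 = 100% and the same person succeeds. Anyone tested at least once has ratio 1.

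**3. What Table 14 would show.** With every participant at the site a success, the displayed proportion is p(1−s) + s. The level at the other three sites that yields a displayed 80% is (0.80 − s)/(1 − s).

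| Site share | True 80% v 50% displayed as | Difference | DBS level elsewhere that displays as 80% |
|---|---|---|---|
| 10% | 82% v 55% | 27 points | 78% |
| 25% | 85% v 62.5% | 22.5 points | 73% |
| 40% | 88% v 70% | 18 points | 67% |

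**4. The adjusted primary test if everyone at the site succeeds.** The site's own intercept absorbs a stratum with no failures, so the stratum carries no information on treatment. Power is that of the other three sites, with n₁ = 100(1−s) and n₀ = 50(1−s). At s = 25% and 80% v 50%: SE₀ = √(0.21 × 0.04) = 0.0917; SE₁ = √(0.16/75 + 0.25/37.5) = 0.0938; (0.30 − 0.1796)/0.0938 = 1.28; power 90.0%.

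| Control rate | Stated | s = 10% | s = 25% | s = 40% |
|---|---|---|---|---|
| 50% | 96% | 94.4% | 90.0% | 82.8% |
| 55% | 89% | 85.1% | 78.4% | 69.2% |

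Simulation of the adjusted Wald test (3,000 trials per setting, 80% v 50%) gave 93.8%, 90.8% and 83.1%. The decision was the same with the site kept or excluded in every trial.

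**5. The adjusted test if some at the site fail.** In the ITT set, withdrawals before discharge or before the first scheduled test, and participants with no test scheduled, count as failures (SAP 4.5.1, 6.3.1, 6.5.1). Complete success at the site therefore cannot be taken for granted. With 90% success there in both arms, s = 25% and 80% v 50%, simulation (1,500 trials) gave power 85.7% with the site kept and 89.9% with it excluded. A separate run gave adjusted odds ratios of about 3.6 kept and 4.3 excluded. Keeping the site pulls the odds ratio toward 1.

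**6. Analysis sets.** SAP 4.5.1 and 4.5.2 call for maximal-period analyses with and without the site in the Completer set, among others. SAP 6.3.3 admits to that set only participants whose recommended intervals are available, and Table 6 lists a missing schedule as a reason for exclusion. The two do not fit unless the site's entries count as a schedule.

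**The case against.** The problem is disclosed in several places, and the analysis without the site is already planned. Table 16 will show the three-site proportions, intervals and p-value, so the undistorted level will be available. The SAP's sentence on what the trial needs to demonstrate is sample-size rationale and not a decision rule. The denominator reading is also unproven. SAP 6.4 says that the entries went into the recommended-schedule field, and Table 42 has weekly, bi-weekly and monthly rows for this site, so interval-type entries run through Appendix 4 are possible. Finally, moving the exclusion analysis to primary departs from the protocol's all-randomised ITT wording. These points limit the size that can be claimed. They do not make the site's data a measure of adherence, and disclosure does not settle which table governs.

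Three stronger readings are tempting, and the documents do not support them.
- A reader might infer a false-positive primary test. If all at the site succeed, the site adds nothing to the adjusted test; if some fail equally in both arms, the effect is pulled toward no difference.
- A reader might infer that keeping or excluding the site makes no difference to the primary test. That holds only if everyone there succeeds, which the SAP's failure rules do not allow to be assumed.
- A reader might infer an inflated type I error in the secondary fractional model. At a 25% share and with assumed completion distributions, about 10% arises only by combining categorical site from the text of SAP 8 with the absence of robust errors in the SAP 8.2 example code. That code has no CLASS statement. With site numeric, as literally coded, the error is about 2% to 4%; with the robust standard errors named in SAP 8.2 the effect does not occur.

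**Conclusion.** The concern stands and should be fixed. That the primary endpoint is not validly measured at one of four sites follows from the SAP's own text and needs no assumption.

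The size is conditional on an assumed site share and on the entered count serving as denominator. On that reading Table 14 overstates adherence in both arms and shows 22.5 points instead of 30 at a 25% share (27 to 18 points over the range). Power for 80% v 50% is about 90% (94% to 83%) against 96% stated, and about 86% at a 25% share if one in ten at the site fails in either arm. Excluding the site does not restore the stated power; it avoids only the further loss. If the entries are used in some other way, neither size nor direction can be fixed from the documents.

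**What to change.** Before data lock, recover the recommended intervals and change dates from the charts at this site, if they can be found. If not:
- Make the planned ITT analyses without this site (Tables 16 and 19) the primary and main secondary adherence analyses. Site is a randomisation stratum, so the comparison within the other three sites remains randomised.
- Report the all-site ITT result as sensitivity, with a footnote on the site and a statement of how its denominator is derived.
- Document the departure from the all-randomised wording in Protocol 11.1.1 and 11.5, and restate power for the three-site sample.
- Reconcile SAP 4.5.1 and 4.5.2 with SAP 6.3.3 and Table 6 on whether the site can enter the Completer set.
- In the SAP 8.2 example code, add a CLASS statement for site and request the robust standard errors that the text names.

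The cost is a SAP amendment, relabelling of tables already planned, and a chart check at one site. The downside is a smaller primary sample, a less favourable stated power, and a documented change to the primary analysis set in an unblinded study.
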